4.9.3 Laboratory Data

Clinical laboratory data includes the measurements of lab parameters from hematology (including HgbA1C), chemistry, urinalysis and serum pregnancy collected from both central laboratory and local laboratory.

- Laboratory data in summary tables and participant data listings will be presented in the International System of Units (SI units; Système International d'Unités).
- If the same lab test has measurements from both central and local labs at same time point, the one from central lab will be used for analysis in tabulation summary.
- Given the lab measurements' baseline and post-baseline results are collected from different labs (most baseline lab measurements are completed at local labs while most Week 24 lab measurements are collected at central lab), the lab results will not be compared with baseline to investigate the change from baseline trend over time except HgbA1C (%). The HgbA1C is a significant parameter as a measure of diabetes, the change from baseline will be calculated and presented in table.
- All scheduled hematology and chemistry parameters' normality assessments will be summarized by visit for each treatment cohort and overall. The assessments will be classified "Normal", "High" and "Low" with respect to the parameter-specific reference ranges established in central lab; and classified as "Normal" and "Abnormal" (with "clinically significant" information) compared to reference ranges by investigator in local lab. The local labs don't collect reference ranges in eCRF, then the status of "High" or "Low" can't be derived programmatically for measurements from local lab, so the summary will be a mixture of assessment values from both central lab and local labs. The number and percentage of participants in each assessment category will be provided.
- All laboratory data will be presented in participant data listings with normality assessments included. The laboratory measurements identified as abnormal (ie, outside the normal range) will also be listed separately by participant, laboratory category, lab parameters at relevant time points.

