1 Vital signs are collected at the Screening/Baseline, Week 3, and Week 24 visits and weekly in conjunction with study drug administration from Baseline through Week 24. Vital signs collected at in-clinic visits (Screening/Baseline, Week 3, Week 24) include systolic and diastolic pressure, respiratory rate, heart rate, temperature, and weight. Height is measured at Screening/Baseline Visit only. If significant weight change is reported or suspected at any point during the study, the SI may choose to collect an additional in-clinic weight at their discretion. During each weekly infusion, vital signs associated with the infusion (systolic and diastolic pressure, respiratory rate, and heart rate) are to be measured pre-infusion, 30 minutes (\pm 5 mins) after the start of infusion (SOI), 60 minutes after the SOI (\pm 10 mins), and 90 minutes (\pm 10 mins) after the SOI. If a participant requires a 90-minute infusion duration due to receiving more than 2 bags of study drug, an additional vital signs measurement is to be completed approximately 30 minutes (\pm 10 mins) after the end of the 90-minute infusion.

2 Clinical safety labs include hematology (CBC with differential), complete chemistry panel and urinalysis at Screening/Baseline, Week 3, and Week 24. Hb A1C will be included in labs at Screening/Baseline and Week 24. If labs are abnormal at Week 3, they may need to be repeated per investigator judgement. Serum pregnancy testing will occur in women of child-bearing potential at the Screening Visit and as necessary during the study. Pregnancy testing is only repeated as applicable if there is a concern for pregnancy. All urine samples must be collected prior to IP administration. Clinical safety labs may be drawn at the study site or obtained at a local site convenient for the participant. Clinical safety lab results obtained locally may be used to assess participant eligibility.

3 Infusion-related AEs are documented weekly in conjunction with study drug administration from Screening/Baseline through week 24

4 The weight collected at the Screening/ Baseline clinic visit will be used to calculate the participant's initial dose. The participant will remain on a stable dose until the next in-person visit when weight be collected, at which point the dose may be adjusted if the participant's weight has increased or decreased by 2kg. Additional information on dose adjustments is included in section 6.7.4 Dosing Changes.

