4.1.2 Windowing, Unscheduled Visits and Repeat Test Results

All assessments collected at scheduled and unscheduled visits will be included in the by-participant data listings.

For Safety endpoints, the data will be analyzed according to the nominal visits except Baseline which is defined as last available value prior to the first dose of study treatment. The results collected at scheduled visits per

protocol will be included in the by-visit summary tables. For laboratory data analysis at the scheduled visits, central-laboratory values will (preferentially) be selected for a given visit; however, if there is no non-missing central-laboratory value available and there is a non-missing local-laboratory value collected at the visit, then a local-laboratory value will be used.

In addition, for Safety endpoints of laboratory data, vital signs and C-SSRS assessments, the last assessment during the post-baseline period will also be summarized using the analysis visit name “End of Treatment Period”, which is defined as the last measurement from all post-baseline visits including the unscheduled visits and early termination visit.

For Efficacy and Biomarker endpoints, the protocol defined visit windowing in Table 3 will be used to window the unscheduled visits or early termination visit to scheduled visit when it doesn’t exist. If unscheduled visits or early termination assessments fall in the same window, then select the assessment closest to the target assessment day. If there are two assessments that fall into a visit window and are equidistant from the target assessment day, then the later assessment will be selected.

Table 3 Analysis Visit Windows for Efficacy (ALSF-R, SVC, ALSAQ-40) and Biomarker

Analysis Visit	Nominal Day	Lower Limit	Upper Limit
Baseline	1	None	Time of first dose of study treatment
Week 3	22	19	25
Week 12	85	78	92
Week 24	169	155	183

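### HbA1c is exempted from the SAP's no-change-from-baseline rule because it is important, not because its local and central values are shown to be comparable, and the planned table does not separate laboratory pairs

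*SAP*

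**What the plan says.** SAP 4.9.3 starts from a limitation: "Given the lab measurements' baseline and post-baseline results are collected from different labs". It describes the pattern as "most baseline lab measurements are completed at local labs while most Week 24 lab measurements are collected at central lab" and draws the consequence that "the lab results will not be compared with baseline to investigate the change from baseline trend over time except HgbA1C". The reason given for the exception is: "The HgbA1C is a significant parameter as a measure of diabetes, the change from baseline will be calculated and presented in table".

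On timing, the footnotes to the Protocol's Schedule of Activities say "Hb A1C will be included in labs at Screening/Baseline and Week 24". (Protocol 6.4.3 names HbA1c in a procedure list shared by Week 3 and Week 24. That small inconsistency does not affect this point.)

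On choosing between sources, SAP 4.1.2 states that "central-laboratory values will (preferentially) be selected for a given visit". If there is no central value at the visit, "then a local-laboratory value will be used". SAP 4.9.3 repeats the preference: "If the same lab test has measurements from both central and local labs at same time point, the one from central lab will be used". Neither section asks that a participant's baseline and Week 24 values come from the same laboratory.

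**The concern.** The reason for withholding change from baseline applies to HbA1c as much as to any other test. Importance is a reason to want a sound comparison. It is not evidence that two laboratories give the same answer. Neither document mentions assay standardisation, cross-calibration, a same-laboratory restriction, a breakdown by laboratory pair or a sensitivity analysis.

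The stake is how the one laboratory change table in the plan will be read. Trehalose is metabolised to glucose (Protocol 1.3.3 and 6.7.8), and diabetes and raised screening glucose are exclusions (Protocol 4.2). Other haematology and chemistry tests receive only normality categories, which mix central and investigator classifications. SAP 4.2 acknowledges that there is no randomised control group, and the historical comparison in SAP 4.7 covers survival, ALSFRS-R and vital capacity, not laboratory data. So nothing in the plan separates a change of laboratory from time on drug. A difference between laboratories could suggest a rise that is not there, or hide one that is.

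**Working it through.** The documents give no SD, no between-laboratory difference and no switching share for HbA1c, so there is no figure of the plan's own to reproduce. The check is mainly textual. The arithmetic only shows scale.

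1. **Does the limitation reach HbA1c?** The schedule footnotes place it at Screening/Baseline and Week 24. SAP 4.9.3 names the same two points as mostly local and mostly central. It does.

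2. **Does the selection rule protect the pair?** Take a participant with a local baseline and both local and central values at Week 24. Under 4.1.2 and 4.9.3 the central value is used, so a local-local pair that exists is analysed as local-to-central. How often both values exist is not stated.

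3. **What enters the mean?** Let d be the true mean change, f the share of participants going from local to central, and b the average central-minus-local difference among them. With no central-to-local pairs, expected mean change = d + f × b. The second term does not shrink as the sample grows.

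4. **Scale, with assumed inputs.** For f = 0.6 to 1.0 and b = 0.1 to 0.3 percentage points:
   - lowest: 0.6 × 0.1 = 0.06
   - middle: 0.8 × 0.2 = 0.16
   - highest: 1.0 × 0.3 = 0.30

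   If the SD of change is 0.3 to 0.5 points (also assumed), the middle case is 0.16/0.5 = 0.32 to 0.16/0.3 = 0.53 of an SD.

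5. **How firm is f?** The word 'most' does not fix it. If a share p is local at baseline and q is central at Week 24, and nobody goes from central to local, then f = p + q − 1. With p = q = 0.8, f = 0.6. With p = q = 0.6, f = 0.2, and the shift is only 0.02 to 0.06. The SAP's statement also covers laboratory measurements in general, not HbA1c alone.

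6. **When does it become noise?** Enrolment is at up to 25 sites, and the schedule footnotes allow samples at a convenient local site, so many local laboratories may contribute. Suppose f = 0.8, with half the switchers at +0.2 and half at −0.2. The mean shift is 0.8 × (0.5 × 0.2 − 0.5 × 0.2) = 0. The variance grows by 0.8 × 0.2² = 0.032, so an SD of 0.3 becomes √(0.09 + 0.032) = 0.35. If all laboratories agree, b = 0 and there is neither shift nor noise.

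7. **How many participants would be in same-type pairs?** At f = 0.6, 0.8 and 1.0 the non-switchers number 28, 14 and 0 of 70 (all planned participants having both values), or 20, 10 and 0 of an assumed 50.

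**The case against.** The strongest reply is that this is one descriptive table in an access protocol, and that the SAP discloses the laboratory change and the exception in the same bullet. SAP 2 plans no formal hypothesis testing, and the default statistics in SAP 4.1 include no confidence interval. HbA1c is grouped with haematology, so it also appears in the by-visit normality summary, the full listings and the separate listing of abnormal values. Adverse events are tabulated too. Individual glycaemic abnormalities can be seen without the mean change. All of this stands, and it limits the weight of the point.

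Several stronger readings are tempting, and the documents do not support them:

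- A reader might infer that the SAP calls the values incomparable. It says only that they will not be compared, and it declares an exception.
- A reader might infer that the HbA1c result will be a laboratory artefact. The documents give neither the size nor the sign of any difference, and differences across many local laboratories may partly cancel.
- A reader might express the harm as lost interval coverage or a false signal rate. No HbA1c interval or test is planned.
- A reader might conclude that local-to-central changes are meaningless, or that only same-laboratory pairs should count. If the laboratories agree, the mixed pairs are sound. Two local values may come from different laboratories. The restricted set could be very small or empty. It may also over-represent remote roll-over participants, whose samples must be collected locally (Protocol 6.2.1) and who may have had trehalose before their EAP baseline.

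What survives is narrower: disclosing the limitation in the SAP does not tell the reader of the table how much of the mean rests on mixed pairs.

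**Conclusion.** The point holds as a matter of presentation and interpretation. SAP 4.9.3 gives a reason not to analyse change from baseline, then sets it aside for HbA1c without showing that the reason does not apply there. The planned mean can carry a local-to-central difference that the design cannot separate from a drug effect.

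Under the assumed inputs the shift ranges from nil (agreement, or differences that cancel) to 0.30 percentage points. These figures depend on the switching share and the between-laboratory difference, neither of which the documents give. No error rate, sample size or primary conclusion is affected. The change is worth making because it is cheap and uses data already collected.

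**What to change.** In SAP 4.9.3:

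- Present HbA1c change from baseline by laboratory pair, with the number of participants in each group and by cohort. Use same laboratory versus local-to-central. If the individual laboratory is not recorded, use local-local and central-central versus local-to-central. Show any central-to-local pairs separately.
- Where baseline is local and Week 24 has both local and central values, use the local Week 24 value for the change calculation. The central preference can stay for the by-visit summary.
- Keep the all-participant change and the by-visit summaries, with a footnote that local-to-central change may reflect the change of laboratory.
- If the sponsor holds evidence that the assays agree, state it there, since it would justify the exception.

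The cost is some SAP wording and one table layout, with no new data collection. The same-laboratory groups will be small and imprecise, and may over-represent remote roll-over participants, so they should sit beside the all-participant result and not replace it. Where the local value is substituted, the mean change will no longer equal the difference between the by-visit means, and a footnote should say so.

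### The by-visit laboratory table mixes two category systems while the laboratory changes from mostly local to mostly central, so High and Low percentages can rise from baseline to Week 24 with no true change

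*SAP*

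**What the plan says.** SAP 4.9.3 plans that for hematology and chemistry the "normality assessments will be summarized by visit for each treatment cohort and overall". Two classifications feed that summary.

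- Central results are Normal, High or Low, "with respect to the parameter-specific reference ranges established in central lab".
- Local results are Normal or Abnormal as judged by the investigator, with clinical significance noted. Local reference ranges are not in the eCRF, so High or Low cannot "be derived programmatically for measurements from local lab".

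The section accepts the consequence, "so the summary will be a mixture of assessment values from both central lab and local labs", and defines the statistic: "The number and percentage of participants in each assessment category will be provided". It does not say what the percentage is a percentage of.

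On where samples were analysed, it reports that "most baseline lab measurements are completed at local labs while most Week 24 lab measurements are collected at central lab". For that reason "the lab results will not be compared with baseline to investigate the change from baseline trend over time except HgbA1C".

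SAP 4.1.2 gives the selection rule: a central value is preferred at a scheduled visit and, if there is none, "then a local-laboratory value will be used". It also adds an End of Treatment Period summary for laboratory data, built from the last post-baseline measurement, with no separate rule on source.

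**The concern.** A local result can never be counted as High or Low, and a central result can never be counted as plain Abnormal. The central share goes from a minority at baseline to a majority at Week 24, so results move between columns because a different laboratory analysed the sample. Read across visits, the table could suggest out-of-range values emerging on treatment, or could hide ones that did.

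This matters somewhat more than usual here. Laboratory tests are a named safety endpoint (SAP 1.1). The historical controls serve only survival, ALSFRS-R and vital capacity (SAP 4.7), so earlier visits are the only comparator for laboratory data. Direction is also of interest: protocol 1.3.3 describes a possibly related liver-enzyme elevation in an earlier study that was reported as a SUSAR. SAP 1 says the results might go into a regulatory submission.

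**Working it through.** The plan states no figure on this point, so there is nothing to reproduce. The check is direct arithmetic.

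**From the documents.** The two category systems, the single mixed summary and the number and percentage per category are in SAP 4.9.3. The central share is known only to be below half at baseline and above half at Week 24; the share at Week 3 is not given. Planned enrollment is about 70 (SAP 6).

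**Assumed.** True rates of High (h) and Low (l) are constant over time, with h from 5% to 20% and l at 5%. Central share c ranges from 0% to 49% at baseline and from 51% to 100% at Week 24. Central flags and local calls are taken to agree on what is normal.

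**Formulas, with all participants assessed at the visit as denominator.**

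- High% = c × h
- Low% = c × l
- Abnormal% = (1 − c) × (h + l)
- Normal% = 1 − h − l, which does not depend on c
- Spurious rise in High + Low = (c at Week 24 − c at baseline) × (h + l)

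**Results (baseline → Week 24, no true change).**

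| True High / Low | Central share | High % | Low % | Abnormal % | Normal % | Rise in High + Low (points) |
|---|---|---|---|---|---|---|
| 5% / 5% | 49% → 51% | 2.45 → 2.55 | 2.45 → 2.55 | 5.1 → 4.9 | 90 → 90 | 0.2 |
| 10% / 5% | 49% → 51% | 4.9 → 5.1 | 2.45 → 2.55 | 7.65 → 7.35 | 85 → 85 | 0.3 |
| 10% / 5% | 20% → 80% | 2 → 8 | 1 → 4 | 12 → 3 | 85 → 85 | 9 |
| 10% / 5% | 10% → 90% | 1 → 9 | 0.5 → 4.5 | 13.5 → 1.5 | 85 → 85 | 12 |
| 10% / 5% | 0% → 100% | 0 → 10 | 0 → 5 | 15 → 0 | 85 → 85 | 15 |
| 20% / 5% | 0% → 100% | 0 → 20 | 0 → 5 | 25 → 0 | 75 → 75 | 25 |

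In the 20% → 80% row, High + Low goes from 3% to 12%. With 70 assessed at both visits that is 0.03 × 70 = 2.1 participants against 0.12 × 70 = 8.4.

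**Masking.** Keep the central share at 20% → 80% and let true High fall from 20% to 5%. The table shows 0.20 × 20% = 4% and then 0.80 × 5% = 4%, so the fall disappears.

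**Exaggeration.** With the same shares, a true rise in High from 10% to 20% shows as 0.20 × 10% = 2% and then 0.80 × 20% = 16%.

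**With source-specific denominators.** High% among participants with a central result is (c × h) / c = h. In the 10% / 5% case, High is 10% and Low is 5% at both visits, whatever the central share.

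**The case against.** The strongest reply is that the SAP already handles the misreading. It names the change of laboratory, declines to compare results with baseline except for HgbA1C, explains why local High and Low are unavailable, and calls the summary a mixture. The labels differ visibly, and a reader who adds High, Low and Abnormal recovers total abnormality at each visit. Abnormal values are also listed by participant, and clinically significant laboratory findings count as adverse events (protocol 10.3.1), so they reach the TEAE tables. No formal hypothesis test is planned (SAP 2).

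Most of that stands and limits the importance of the point. It does not correct the table: withdrawing change from baseline leaves a by-visit display of categories whose availability depends on the laboratory. Total abnormality can be recovered by addition, but its direction cannot.

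Several stronger readings are tempting and are not supported:

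- **A stated common denominator.** A reader might take this as given. It is inferred, and the table shells are in a separate Data Presentation Plan. Source-specific percentages would avoid the artefact.
- **Any rise is purely the laboratory.** The arithmetic shows only that a rise would appear without a true change. A real change could add to it or be hidden by it.
- **High and Low near zero at baseline, or rising at every visit.** The SAP says only that most baseline results are local, and it does not give the source at Week 3.
- **The only by-visit summary of hematology and chemistry.** HgbA1C change from baseline is tabulated. The general rules for continuous variables (SAP 4.1) and for scheduled results (SAP 4.1.2) could also imply numeric summaries.

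**Conclusion.** The point holds as a minor weakness, disclosed but not corrected, in one descriptive safety table. On an all-assessed denominator, and with constant true rates, the direction is fixed by the plan's own description: High and Low go up and Abnormal goes down between baseline and Week 24. The size is unknown. It could be trivial (about 0.2 points at 10% abnormal and a central share of 49% → 51%) or large (25 points at 25% abnormal and 0% → 100%); the middle case of 15% abnormal and 20% → 80% gives 9 points. These figures rest on assumed abnormality rates and shares, and on the unstated denominator being everyone assessed at the visit. The Normal percentage is unaffected provided that the two sources agree on what is normal. No efficacy estimate, test or sample size is involved.

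**What to change.** In SAP 4.9.3 and the matching table shell:

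1. Present normality by laboratory source. Compute Normal/High/Low percentages only over participants with a central result at that visit, and Normal/Abnormal percentages only over participants with a local result.
2. Show the number of central and local results at each visit, including Week 3 and the End of Treatment Period row.
3. Footnote the change of laboratory. The HgbA1C change from baseline may cross the same change and should carry the same note.
4. Optionally add a collapsed Normal/Abnormal row. It adds little beyond what addition already gives, and it needs a caveat that central range flags and investigator-judged local calls may not agree.

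The cost is one revised table shell and no new data. The price is smaller denominators, mainly for central results at baseline: at an assumed 20% share, 0.20 × 70 = 14 participants. The central group at baseline and at Week 24 would then consist largely of different people, so the split removes the category artefact but does not by itself give a clean comparison over time.

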4.9.4 Vital Signs

Vital sign parameters to be summarized include Systolic Blood Pressure (mmHg), Diastolic Blood Pressure (mmHg), Heart Rate (beats/min), Respiratory rate (breaths/min), Temperature (C) and Weight (kg).

Vital signs will be summarized with descriptive statistics by visit and treatment cohort and overall. Descriptive statistics will be presented for results and change from baseline at each visit and time point where parameters were scheduled to be collected. For parameters Systolic Blood Pressure (mmHg), Diastolic Blood Pressure (mmHg), Heart Rate (beats/min), Respiratory rate (breaths/min) at infusion visits, the changes associated with the infusion from pre-dose to 30 mins post start of infusion (SOI), 60 minutes post the SOI, 90 minutes post the SOI, and 30 minutes post end of infusion (EOI) if collected will also be summarized.

